Briefly, the patient sits in a reclining chair with the hands at heart level and propped in a comfortable position such that the fingers are hanging freely. Fingertip probes are placed on both index fingers and pulse wave amplitudes are recorded for the duration of the study. After 5-6 min of baseline measurement, arterial flow to the nondominant arm is occluded for 5 min using a BP cuff inflated to 40 mmHg above systolic pressure. After the 5-min occlusion, the cuff is rapidly deflated to allow for reactive or flow-mediated hyperemia. Pulse wave amplitudes are recorded for at least 5 min after the cuff is deflated. An integrated software program compares the ratio of arterial pressure in the two fingers before and after the occlusion to calculate the RH-PAT score. The RH-PAT score is calculated as the ratio of the average pulse wave amplitude measured over 60 s starting 1 min after cuff deflation to the average pulse wave amplitude measured at baseline. This ratio is normalized to the concurrent signal from the contralateral finger to correct for changes in systemic vascular tone.

Heart Rate Variability: Heart rate variability (HRV) assessment provides a non-invasive and objective method for investigating autonomic input into the heart and measuring cardiac autonomic neuropathy (CAN). We have previously shown it is associated with subclinical atherosclerosis⁷⁷⁻⁷⁹. In addition, studies in T1D youth demonstrated reduction in HRV⁸⁰, mostly with vagal withdrawal early⁸¹ and sympathetic dysfunction later in the disease process⁸². However, our large study found overall HRV reduction suggesting a more advanced state of cardiac autonomic neuropathy^{77,78}. Therefore HRV analysis is expected to find abnormalities already occurring in T1D youth. The measurement quantifies the amount by which the R-R interval or heart rate changes from one cardiac cycle to the next, and can be assessed either by time-domain analysis or by spectral analysis (frequency-domain analysis) of ECG recordings. HRV will be assessed in supine subjects over a 5 minute period of rest, and then during 5 minutes of deep breathing. Following another 5 minute baseline period before each session, responses to standing and Valsalva breathing will be measured. Tachycardic and bradycardic extremes are identified and the difference used as a measure of CAN.

MRI: The MRI will be obtained during visits 4 and 7 at the UCD Brain Imaging Center on the Anschutz campus or at the CHC Radiology Department. The purpose of the thorax MRI is to obtain phase contrast imaging through several levels of the aorta, including the ascending aorta, the transverse arch, and the descending aorta and renal vessels, as well as the heart. MRI images will be taken supine of the thorax during normal breathing, as well as during inhalation and exhalation. These dicom images will be transferred from the MRI to an off-line processing system, MatLab, where the contours of the PC images will be carried out in order to determine the flow pattern and wall shear stress.

DEXA: Body composition will be measured using the DEXA technique on the adult and pediatric CTRCs and will be used to derive fat-free mass and % body fat. This technique relies on the absorption of dual electron wavelengths for the assessment of body fat, lean tissue, and bone mineral density.

Indirect calorimetry: For measurement of RQ fasting and during low infusion rate to assess insulin response of shift from fat to carbohydrate metabolism.

Waist Circumference: Measurements from phase 1 and 2 will be used in an insulin sensitivity prediction equation.⁹⁰

Sleep questionnaires: The Epworth sleepiness scale for adults⁸³ and the adult Sleep Hygiene Scale^{84,85} will be completed by adult participants to obtain information on behavioral sleep variables as in our ongoing sleep study in PCOS. Adolescent participants will complete the Cleveland Adolescent Sleepiness Questionnaire, the Sleep Disturbances Scale for Children, the Adolescent Sleep Hygiene Scale and the Behavioral Sleep Medicine Clinic Sleep Questionnaire. Through this study we will also collaborate with [name], Pediatric Sleep expert (University of Colorado, Denver) who has extensive experience with these questionnaires and the Actiwatch sleep monitor, and is available for consultation on the proposed project as needed.

Sleep/wake and activity monitoring: Typical home sleep and activity patterns will be monitored for one week using actigraphy^{86,87}. The Actiwatch Spectrum Plus (Philips Resironics, OR) will be worn on the non-dominant wrist and will collect data on movements and light exposure in 1-min bins. A concurrent sleep diary will be completed by participants to allow for removal of artifacts (e.g., failure to wear the actigraphy during a portion of the night). Average sleep start and end time, sleep duration, and sleep efficiency will be examined. Participants will be asked to refrain from caffeine, non-steroidal anti-inflammatory drugs, and alcohol during the sleep monitoring period.

Hypoglycemia questionnaires: Hypoglycemia awareness will be assessed using the Gold method (Question: "Do you know when your hypos are starting?" response on 7 point Likert scale), Clarke method (8 question questionnaire), and the McAuley score (list of symptoms with a 7 point Likert scale for each)⁶⁴⁻⁶⁷.

D. Description, Risks and Justification of Procedures and Data Collection Tools:

Potential risks:

BCQR intervention: Bromocriptine itself has been available and widely used for Parkinson's Disease and prolactinoma for decades. It was also used for a time for congestive heart failure. The quick release formulation is so far apparently similar in safety and tolerability. Common side effects include mild hypotension, mild fatigue/somnolence, headache, depressed mood, insomnia, nausea, and diarrhea. Less common and more serious side effects have been seen with BCQR including hypersensitivity reactions, hypoglycemia and syncope. There is no increase in CVD. In fact studies so far indicate a protective effect. Bromocriptine is standardly used in young children, adolescents, and adults of all ages with hyperprolactinemia at higher doses than proposed in our study and should be well tolerated. Frequent blood sugar monitoring and contact with study staff will help avoid hypo- or hyperglycemia. Potential benefits include improved glycemic control and decreased insulin requirement, as well as metabolic and vascular benefits related to decreased chronic SNS activity, decreased renin angiotensin system activation, and resetting of the circadian rhythm. Subjects will be withdrawn if they are unable to tolerate the minimum acceptable dose of BCQR (1.6mg QD) or if they experience a predefined serious adverse event (infection related to blood draw or IV placement; severe hypoglycemia during the mixed meal tolerance test (blood glucose < 45 mg/dl), more than one episode of severe hypoglycemia requiring assistance or diabetic ketoacidosis (DKA) while on study drug or other severe reactions possibly or probably related to the study drug). No further data will be collected from withdrawn subjects. All SAEs will be followed until resolution.

Blood Samples: The collection of blood samples may result in temporary discomfort, bruising, bleeding, and on rare occasions, infection. EMLA cream helps to prevent discomfort, and sterile technique helps to minimize these risks.

IV risks: There is temporary discomfort when the needle goes in and 10% of the time there is a small amount of bleeding under the skin that may produce a bruise. Rarely, there is a risk of a blood clot forming or infection. EMLA cream helps to prevent discomfort and sterile technique by experienced CTRC nurses helps to minimize these risks.

Study Diet: There is a small risk that blood sugars will be higher or lower than normal at home while eating the study diet as it may differ from the subject's usual diet. To avoid this risk, subjects will be asked to monitor their blood sugars at least four times a day while on the study diets and following procedures. Carbohydrate content will also be provided for each food item to assist with carbohydrate counting.

Continuous Glucose Monitoring (CGM): A continuous glucose sensor will be placed (Dexcom G4 Platinum, Dexcom, Inc., San Diego, CA) to assess home blood glucose values. The sensor is well tolerated with the only side effects being mild to moderate site irritation in 2% of patients, and in rare cases, skin infection.

DEXA Scan: There is no pain with this procedure. For females, a urine pregnancy test will be checked prior to the test to avoid any x-ray exposure to a pregnant person. This procedure involves the use of X-rays. The amount of radiation exposure during the DEXA test is approximately 15 mSv which is 7 times the level of background radiation in Colorado or approximately equal to the amount of radiation a subject would receive being outdoors in Denver for two days.

Mixed meal tolerance test: There is a small risk that blood sugars will be higher or lower than normal at home while eating the study diet and with the mixed meal tolerance test (MMTT) as it may differ from the subject's usual diet. To avoid this risk, blood sugars will be checked before and after the meal and additional carbohydrate or insulin given as indicated.

Ansar Heart rate variability, Endopat and Dynapulse: There are no significant risks associated with these procedures. There may be slight discomfort when the blood pressure cuff is inflated.

MRI: The MRI is a non-invasive scan. MRI uses a magnet and there is no radiation and no risk involved with the MRI. The scan may be loud, therefore participants may be provided with audio protection and optional television. Metal cannot enter the MRI area. Participants will be screened to assure no metal is present prior to MRI.

Indirect Calorimetry: The subject may feel claustrophobic.

Waist Circumference: There is no risk associated with measuring waist circumference

Data handling: Data will be examined for completeness and errors during data cleaning, in order to remove any spurious or incorrect data and complete any missing data in the database where possible. Protocol deviations will be reported to COMIRB and the study Safety Officer within 30 days of the deviation. Deviations from the original statistical analysis plan will be reported to COMIRB with the next continuing review and disclosed in any publication resulting from this study.

Assessment of Safety: Safety parameters will include monitoring of any adverse events (AEs) or serious adverse events (SAEs), including number of hypoglycemic episodes and percentage of time spent hypoglycemic during the last week of CGM data. Safety parameters will be obtained by questionnaire at each visit, and will include reports of any AEs or SAEs.

At each visit, study subjects will be asked if they have had any AE, including illness, injury or hospitalization since the last visit. If so, the onset date, resolution date, severity and outcome will be recorded. All AEs will be reviewed by the PIs and a determination of SAE or AE status will be made. All SAEs will be reported to the IRB, safety officer, and sponsor following regulations. Bromocriptine is less well studied in adolescents and therefore further assessment of Bromocriptine's hypotensive effect will be monitored at each visit for adolescents aged 12-17 via orthostatic measurements. Assessment of intercurrent illnesses will be made by asking study participants of any illnesses or symptoms they have had since the prior visit, onset date and resolution date, severity and outcome of the illness. Subjects with SAEs will be followed until resolution of the event. All other subjects with AEs will be followed until the end of the study.

Study stopping and subject discontinuation criteria: The trial will be stopped if >2 subjects meet criteria for individual subject discontinuation [≥ 2 hypoglycemic events requiring assistance or diabetic ketoacidosis (DKA) during a study phase] or if >2 subjects experience a serious adverse event (SAE) possibly or probably related to the study drug. Subjects will be withdrawn if they are unable to tolerate the minimum acceptable dose of BCQR (1.6mg QD) or if they experience a predefined SAE [infection related to blood draw or IV placement; severe hypoglycemia during the MMTT (blood glucose < 45 mg/dl), more than one episode of severe hypoglycemia requiring assistance or DKA while on study drug or other severe reactions possibly or probably related to the study drug]. No further data will be collected from withdrawn subjects. As some withdrawals are accounted for in the recruitment plan, there will be no specific replacement of withdrawn subjects. SAEs will be followed until resolution. Otherwise, withdrawn subjects will follow up with their care providers.

E. Potential Scientific Problems:

Interpretation of results: Based on the basic and clinical literature for BCQR, we expect that BCQR will reduce HGP and lipolysis throughout the day, effectively improving insulin action and reducing glycemic variability, improving glucose tolerance and control as evidenced by lower CGM-glucose and glucose AUC during MMTT, and/or decreasing insulin dose. Any of these results would support the use of BCQR as adjunct therapy in T1D. In addition, the presumed mechanism of BCQR supports an expectation of decreased vascular stiffness and improved endothelial function. These results would further support use of BCQR in T1D, even independent of glycemic benefits, as CVD risk reduction is an important goal in T1D with long term benefits in health outcomes, quality of life, and lifetime medical costs. We further speculate that the effects on sympathetic activation and circadian rhythm may improve sleep quality (thus further improving insulin sensitivity), blood pressure, hypoglycemia awareness, and thus hypoglycemia frequency and/or severity.

Pitfalls and limitations: This is a fairly ambitious study with a large planned cohort to allow subgroup analyses for potential targeting of this novel intervention. However, we have been successful individually and in collaborations in recruiting for T1D studies with far more burdensome and invasive outcomes, including OGTT, echocardiograms, exercise testing, 1-2 day overnight admission, overnight insulin drip (DM subjects), hyperinsulinemic insulin clamp with muscle biopsy, multiple study diets, medication interventions, brachial artery and carotid ultrasound, and hepatic MRI paired with muscle lipid MRS. Our preliminary studies used adolescents and adults and techniques similar to the proposed protocol, establishing the necessary complex procedures and collaborations to complete this study: (1) The PI's are experienced in randomized, double blinded clinical trials in T1D adolescents and adults. This depth of experience makes the interventional component likely to be highly successful. (2) The University of Colorado's recently re-funded Clinical and Translational Research Center has the facilities needed for all of the visits and the investigators own the equipment required. (3) Our preliminary data demonstrate the feasibility of the proposed studies in youth and adults, our ability to perform the proposed studies, compelling reasons for further study and the productivity of the PI's. (4) The Barbara Davis Center for Childhood Diabetes is a large, tertiary care center for type T1D, with approximately 3000 youth and 2500 adults with T1D. The PI's are able to recruit from all patients seen at the BDC, in addition to clinics at the University, and Children's Hospital making recruitment feasible. Likewise, we have previous experience recruiting from these demographics for similar studies. To limit drop-out, we maintain frequent contact with participants, use incentives for visits and adherence, and "surprise" incentives such as sports tickets and raffles to maintain contact with the study team. We find these strategies successful for maintaining compliance in our study participants. Due to our TODAY, RISE, and other metformin studies, our staff is experienced with long-term adolescent and adult diabetes studies, with excellent study retention for as long as ten years.

While the brachial artery ultrasound is considered by some to be the gold standard technique for endothelial function, its notorious user-dependence introduces more variability for repeated measures. The Endo-PAT device is also noninvasive, much simpler to use and is performed and analyzed in a standard way that allows comparability within subjects. Simultaneous assessment of the contralateral finger also allows an internal control not present with ultrasound, and therefore we will assess endothelial function with EndoPAT as in our most recent studies. In addition, while the hyperinsulinemic euglycemic clamp is the gold-standard measure of insulin sensitivity, our estimated measures correlate well with the gold standard and will help reduce invasiveness and cost and improve the feasibility and sample size of the study.

Multiple confounders can affect IR and glycemic control. We will control or adjust for these as possible using standard methods. Subject activity and diet that affect IR will be addressed by prescribing a standardized study diet (with carbohydrate content labeled for counting) and limiting strenuous exercise for 3 days prior to the MMTT visits. Stage of menstrual cycle will also be controlled for as hormonal status in females influences vascular measures, IR and circadian rhythms. Finally, use of CGM will help limit hypo- and hyperglycemia during the trial.

F. Data Analysis Plan:

Planned enrollment: 133 T1D subjects (50% male) will be enrolled with the goal of completing 80 (see power analysis below).

Power and Sample Size: Power analysis and sample size are based on expected changes from the literature and from preliminary data for the primary outcomes for each aim. The sample size for the entire study was based on the power analysis for the subgroup analyses by age, in order to ensure adequate power to detect clinically meaningful treatment effects within each subgroup. In addition, we plan to examine the results by other characteristics (e.g. by obesity level, positive c-peptide status, etc.) in exploratory analyses which are not fully powered, but which may provide insight into heterogeneity in response to the therapy, thus guiding a future clinical trial if results of this study are positive. Desired α is set at 0.05. Since data used for this analysis are from within-subjects comparisons, repeated measures analysis will be used to compare outcome variables after each treatment (placebo, BCQR), adjusting for the randomization assignment of treatment order.

Assessment of Efficacy

The primary efficacy parameters will be change in insulin dose and CGM mean glucose on treatment versus placebo. Secondary efficacy measures will include change in post-MMT glucose and insulin AUC, and change in other CGM parameters (SD, %hyperglycemic, % hypoglycemic). Total daily basal and bolus insulin dose will be obtained at screening, and then at time zero for each medication phase. Insulin diaries will be obtained during the last week of each phase. Change in total, basal, and bolus insulin dose in units per day and total insulin in units per kg per day will be examined between medication phases to determine whether insulin requirements were lower at the end of the BCQR phase than the end of the placebo phase. Similarly, change in mean CGM glucose from the last 2 weeks of each medication phase will be examined to determine if overall mean glucose is decreased while on treatment versus placebo.

Analysis Plan: All randomized subjects will be included in the analysis using an intention to treat analysis. The change in insulin dose, CGM-glucose and other metabolic parameters will be compared between the placebo and treatment visits in each subject using paired t-tests for univariate comparisons, and using repeated measures linear regression to adjust for covariates including age, diabetes duration, baseline HbA1c, and BMI. An interaction term will be entered into the model to examine whether the effect of treatment on either outcome differs among adults linearly by age, and if there is a significant interaction ($p<0.10$), results will be stratified by age group. We will also use interaction terms to assess whether the effect of treatment differs by BMI. We will also examine whether diabetes duration and initial HbA1c have an effect on outcomes by testing for an interaction between these continuous variables and the change in insulin dose and CGM-glucose. Change in vascular parameters will also be examined using paired t-test and repeated measures regression to determine if the treatment with BCQR affects vascular stiffness or function.

SA1: Effect on metabolic parameters (insulin dose, mean glucose and glycemic variability by CGM, postprandial glucose AUC by MMTT): While there are no published data on the effect of BCQR on insulin dose, prior data on the effect of Metformin⁸⁸ indicate that the change in daily insulin dose is normally distributed with standard error of 2.2 units (SD 7.6) and data from prior studies in adults with T1D performed at our center indicate that the change in total daily insulin dose

over 4 weeks is normally distributed with a standard deviation of 15 – 18.8 units/day. Assuming a SD of 18.8 to be conservative, we will be able to detect a true change in the daily insulin dose of matched pairs of \pm 5.9 units/day with 80% power in the overall group (n=80) and a change of 8.3 units/day within each age group (n=40). In a prior study of the efficacy of BCQR in adult patients with T2D, study participants treated with BCQR experienced a decrease in fasting plasma glucose level of 36.09 mg/dl and a decrease in post-prandial plasma glucose of 14.38 mg/dl after 12 weeks of treatment⁸⁹. In the overall study group, we will be able to detect a change in CGM-glucose of 3.1 mg/dl with 80% power in the entire study group and a change in CGM-glucose of \pm 4.4 mg/dl in each age group, assuming an SD of 10.03 mg/dl.

SA2: Effect in sub-groups: For comparisons of change in insulin dose and CGM-glucose by group in two-sample independent comparisons assuming equal variance and using estimates of SD as in SA1, we will have 80% power to detect a difference in the effect of BCQR treatment on daily insulin dose of \pm 11.9 units/day, and a difference in change in CGM-glucose of \pm 6.4 mg/dl. For evaluation of BMI and age as continuous variables, we will have 90% power to detect a correlation coefficient of 0.307 or greater in the overall group in univariate analysis, and a slope of 0.32 for daily insulin dose or 0.37 for BMI in linear regression analysis.

SA3: Effect on vascular measures: Change in measures of vascular health (BrachD and RH-PAT RHI as primary outcomes, AI and HRV as secondary outcomes) will be compared following placebo and treatment with BCQR. In a prior study of BrachD in healthy adolescents and young adults, BrachD was normally distributed with a SD ranging from 1.04 to 1.29. We will have 80% power to detect a difference in BrachD of 0.343 mmHg⁻¹ in the entire study group, and a difference of 0.60 mmHg⁻¹ in each age group⁵⁵. A prior study in children with T1D found an intrapatient standard deviation of 0.261 for RH-PAT RHI. Assuming this intrapatient standard deviation, in the overall group we will have 80% power to detect a change in RH-PAT RHI of 0.10% between treatment and placebo visits, and 0.10% in each age subgroup (adolescents and adults).

G. Summarize Knowledge to be Gained: BCQR has shown promise in type 2 diabetes as an oral antglycemic agent that is generally well tolerated and safe and has a novel mechanism with the potential to have significant independent benefit for vascular complications. Studies so far have shown a dramatic decrease in cardiovascular events in type 2 diabetes. The mechanism and our current understanding of T1D suggest that BCQR may also benefit individuals with T1D in terms of glycemic control, insulin resistance, and vascular complication risk. This study will provide preliminary data supporting or refuting the hypothesis that BCQR is a novel oral agent that will benefit glycemic control, vascular function and stiffness, and hypoglycemia awareness in T1D.

H. References:

1. DeFronzo RA. Bromocriptine: a sympatholytic, d2-dopamine agonist for the treatment of type 2 diabetes. *Diabetes Care*. Apr 2011;34(4):789-794.

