SA#1: To test the hypothesis that BCQR will improve clinical parameters of insulin action in T1D (insulin dose, mean glucose and glycemic variability by continuous glucose monitoring [CGM], postprandial glucose excursion by glucose and insulin area under the curve during MMTT). We further hypothesize that (1) these benefits will incur due to improved postprandial suppression of glucagon and lipolysis and (2) the decrease in chronic SNS tone will lead to improved SNS responsiveness to hypoglycemia, with beneficial effects on hypoglycemia awareness and counter-regulatory response (hypoglycemia awareness questionnaire) and susceptibility to hypoglycemia (CGM).

SA#2: To investigate clinical parameters that may predict response to BCQR in order to allow targeted use of this intervention if appropriate. Subgroup analyses will be performed by age, BMI and estimated insulin sensitivity. Multivariate modeling will address other potential predictors including C-peptide, fasting NEFA, baseline HbA1c, sex, sleep characteristics, circadian rhythm delay.

SA#3: To test the hypothesis that BCQR-induced reduction in SNS activation, NEFA levels, and vascular IR will improve vascular function (arterial stiffness by Dynapulse and endothelial function by EndoPAT) and decrease blood pressure.

II. Background and Significance:

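### Estimated insulin sensitivity is named for subgroup analysis in SA#2 but, unlike age and BMI, has no continuous or interaction analysis; a median split would cost about 18 to 20 points of power

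*Combined protocol and SAP*

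**What the plan says.** Specific Aims, SA#2, lists three characteristics together: "Subgroup analyses will be performed by age, BMI and estimated insulin sensitivity". The next sentence sends a different set to modelling: "Multivariate modeling will address other potential predictors including C-peptide, fasting NEFA, baseline HbA1c, sex, sleep characteristics, circadian rhythm delay". eIS is not in that set.

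Section F, Analysis Plan, then specifies effect-modification tests. For age: "An interaction term will be entered into the model to examine whether the effect of treatment on either outcome differs among adults linearly by age". For BMI: "We will also use interaction terms to assess whether the effect of treatment differs by BMI". For two further variables: "We will also examine whether diabetes duration and initial HbA1c have an effect on outcomes by testing for an interaction between these continuous variables". eIS is not mentioned.

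Section F, SA2: Effect in sub-groups, gives two kinds of power statement. The first is "For comparisons of change in insulin dose and CGM-glucose by group in two-sample independent comparisons assuming equal variance", with detectable differences of 11.9 units/day and 6.4 mg/dl at 80% power. The second is "For evaluation of BMI and age as continuous variables, we will have 90% power to detect a correlation coefficient of 0.307 or greater". Neither names eIS.

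Section III, Estimation of IR in T1D, gives eIS-CACTI as the exponential of a linear combination of waist, daily insulin dose per kg, triglycerides and diastolic pressure. It offers no cut-point. Section IV.A limits the SA#2 primary outcome to the impact of age and BMI.

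**The concern.** Of the three characteristics named for subgroup analysis, eIS is the only one with no stated continuous or interaction test. Age at least has a ready adolescent/adult boundary; the plan gives none for eIS. If eIS is handled by the one subgroup method described, the variation in eIS within each group is thrown away and the answer depends on where the line is drawn. If it is handled some other way, the method and any cut-point are left open until the data are in hand.

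SA#2 is meant to support targeted use of BCQR, and insulin resistance is the mechanism on which the trial rests. A real gradient of response across eIS could be missed, or could appear or vanish with the choice of cut.

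**Working it through.** **Inputs.** 80 completers (Section F, Planned enrollment); alpha 0.05 (Power and Sample Size; two-sided assumed, as the plan does not say); SD of change 18.8 units/day and 10.03 mg/dl, and 40 per age group (SA1); r = 0.307 at 90% power (SA2).

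**1. The plan's two-group figures.** With 40 per group, the detectable difference is (1.960 + 0.842) × SD × √(2/40). For insulin dose, 2.802 × 18.8 × 0.2236 = 11.8 units/day; the t-based value is 11.92. For CGM glucose the values are 6.28 and 6.36 mg/dl. The stated 11.9 and 6.4 reproduce.

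**2. The plan's continuous figure.** Power = Φ(atanh(r) × √(n − 3) − 1.960). At r = 0.307 and n = 80: atanh(0.307) = 0.317, times √77 = 8.775 gives 2.784, less 1.960 gives 0.824, so power is 79.5% (81.3% by a t-based calculation; 87.3% if one-sided). The stated 90% does not reproduce. It needs r = 0.353 at n = 80, or about 108 completers at r = 0.307. Both values of r are carried forward.

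**3. Cost of cutting a normal score.** Splitting with a proportion p in one group multiplies the correlation by φ(z_p)/√(p(1 − p)). At the median this is 0.3989/0.5 = 0.798, so 0.307 becomes 0.245 and 0.353 becomes 0.282. The formula in step 2 then gives, for n = 80:

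| Analysis | Factor | Power, r = 0.307 | Loss (points) | Power, r = 0.353 | Loss (points) |
|---|---|---|---|---|---|
| Continuous | 1 | 79.5% | – | 90.0% | – |
| Median split | 0.798 | 59.3% | 20.2 | 72.0% | 18.0 |
| 1/3 v 2/3 | 0.771 | 56.3% | 23.2 | 69.0% | 21.0 |
| 25/75 | 0.734 | 52.1% | 27.4 | 64.4% | 25.6 |
| 20/80 | 0.700 | 48.2% | 31.3 | 60.1% | 29.9 |

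**4. Simulation check (20,000 trials, r = 0.307).** Continuous 79.7%, median split 60.0%, three-group ANOVA on tertiles 58.8%, tertile trend 69.6% (loss about 10 points). With a lognormal score (log-SD 0.4), continuous 78.9% against median split 54.3% (loss about 25 points).

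**5. Dependence on effect size and n.** At n = 80 the median-split loss is 13.6 points at r = 0.20, 18.4 at 0.25, 20.3 at 0.30, 18.2 at 0.35 and 13.4 at 0.40. It is 8 points or less at r ≤ 0.15 or r ≥ 0.45. With 40 completers and r = 0.307, power is 48.8% continuous against 33.0% split, a loss of about 16 points.

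**The case against.** A reader might infer from SA#2 that the plan commits to dichotomising eIS. The documents do not support that. No section gives a cut-point, a number of groups or a test for eIS. Age and BMI stand in the same subgroup sentence and are still analysed continuously, so the word subgroup does not by itself mean grouped only. The two-sample sentence in Section F does not name eIS either, and its figures reproduce with 40 against 40, the age-group sizes. Using 11.9 units/day as a benchmark for eIS would be the reader's step, not the plan's.

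A reader might also infer that eIS is a leading predictor in this trial. Section IV.A names only age and BMI for the SA#2 primary outcome, the hypothesised modifiers in the opening summary do not include eIS, and Power and Sample Size describes analyses by other characteristics as exploratory and not fully powered. Fuller treatment of age and BMI fits that hierarchy.

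Finally, a continuous analysis does not solve everything. eIS-CACTI contains daily insulin dose per kg, and insulin dose is a primary outcome, so an interaction on insulin dose carries a built-in association however eIS is modelled.

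All of this stands, and it limits the claim. What it leaves is that the analyses of age and BMI are written down and that of eIS is not.

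**Conclusion.** The point holds as an unspecified analysis with a better method close at hand. eIS is a continuous score named for subgroup analysis, with no continuous or interaction test, in a plan that supplies one for four other continuous variables.

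The power cost is conditional on how eIS would be grouped. For a median split it is about 18 to 20 points at r = 0.31 to 0.35, assuming 80 completers, two-sided alpha 0.05, a roughly normal score and a linear relation. It is about half that for a tertile trend, larger for uneven splits or a skewed score, and small when the association is very weak or strong. The values of r are those relevant to the plan's statement for age and BMI; the plan gives none for eIS.

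The stated 90% power at r = 0.307 needs correcting in its own right: with 80 completers it is about 80%. The eIS analysis is secondary, so this should be changed but does not threaten the main comparison.

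**What to change.** - In Section F, Analysis Plan, add eIS to the variables tested by interaction, as a treatment-by-eIS term with eIS continuous. Add eIS to the continuous-variable sentence under SA2, and align the SA#2 aim.
- Name the equation. Section III refers to equations for both youth and adults, so choose one for all, or one per age cohort on a common scale.
- Calculate eIS from pre-treatment values. The Waist Circumference paragraph takes measurements from phases 1 and 2 without fixing the time point, and a value taken on treatment could itself be changed by BCQR.
- Read the insulin-dose interaction with the shared dose component in mind, and consider the CGM-glucose interaction alongside it.
- Use eIS groups, or estimated effects at the 25th, 50th and 75th percentiles, for description only.
- Correct the SA2 power sentence: about 80% at r = 0.307, or 90% at r = 0.353, for 80 completers.

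The cost is plan wording, plus confirming that the equation's components are recorded before the first dose. The one analytic downside is the assumed linear, or simple curved, relation, which a plot can check.
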